10.3 Clinical laboratory evaluations

Laboratory evaluations will be analyzed in the SS for observed cases, where all data is included.

Measurements outside the clinical reference ranges will be assessed by the investigator. In addition, laboratory values will be graded (where possible) according to CTCAE Version 5.0.

All laboratory data will be listed by participant and time point including changes from Baseline and percentage changes from Baseline for numeric variables, as well as flags for measurements outside the normal ranges (to flag markedly abnormal results).

Values that are below the lower limit of the reference range will be flagged as 'L' (low) and values that are above the upper limit of the reference range will be flagged as 'H' (high). The flag and the CTCAE grade will be included in the listings.

Any laboratory parameters that are given as '<xx' or '>xx' in the database will be imputed with the absolute value of the number without the sign (<2.2 will be imputed as 2.2) for the calculation of the changes from Baseline.

Summary tables will be provided for both absolute values, changes from Baseline and percent changes from Baseline. Shift tables by markedly abnormal lab parameters (see Section 13.18) will be presented for clinical chemistry, hematology parameters. For each of clinical chemistry and hematology, there will be:

- One table for lab parameters that have marked abnormal value based on values that are <LLN. This table will show the number and percentage of participants who have a marked abnormal value at any time of the study post Baseline compared to Baseline
- One table for lab parameters that have marked abnormal value based on values that are >ULN. This table will show the number and percentage of participants who have a marked abnormal value at any time of the study post Baseline compared to Baseline

The denominator for the percentages in both types marked abnormal lab value shift tables will be the number of participants in the SS.

The number and percentage of participants with a treatment-emergent markedly abnormal result will be presented for each parameter where markedly abnormal criteria are defined, by visit and treatment group, including a tabulation of incidence at any post-BL time point (regardless of visit).

Urinalysis and urine sediment results will be listed.

Furthermore, figures will be provided both for the mean value by visit and for the mean changes from Baseline by visit for continuous laboratory parameters (as observed).

The urinary albumin: creatinine ratio (mg/mmol) and urinary protein: creatinine ratio (mg/mmol) will be calculated by the laboratory from the corresponding urinary albumin, protein and creatinine measurements obtained at Visit 1 (Screening) to 15/EOS (Week 54). A summary table showing descriptive statistics for the change from Baseline values by visit for urinary protein: creatinine ratio and urinary albumin: creatinine ratio will be provided for the subset of participants with a urinary protein: creatinine ratio >56mg/mmol at Baseline.

Laboratory results for participants meeting the criteria for potential drug induced liver injury (see Figure 7-1 in the protocol) will be displayed in a table and a listing. A listing for participants who meet Hy's Law Criteria will also be provided.

HIV test at Screening, hepatitis test at Screening and Tuberculosis test are done as part of the inclusion/exclusion criteria, therefore, they will only be listed.

Local laboratory results are only required in the event that the central laboratory results are not available in time for either study treatment administration and/or response evaluation. If a local sample is required, it is important that the sample for central analysis is obtained at the same time. Additionally, if the local laboratory results are used to make either a study treatment decision or response evaluation, the results must be entered into the eCRF. If central labs are unavailable, local labs will be utilized for evaluating the efficacy response (such as BILAG). However, the findings from local labs will only be included in listings and not in safety summaries.

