- If study participant has a result of ALT, AST, or ALP that is >ULN but that does not meet the exclusion limit at Screening, a repetition of the lab assessment is recommended to judge the dynamic of the increase, but is in the Investigator's discretion, considering the medical history of the participant. In case of a further clinically relevant increase (with a value that still doesn't meet the exclusion limit), inclusion of the study participant must be discussed with the Medical Monitor.

30a. Study participant has chronic kidney failure stage 4, manifested by estimated glomerular filtration rate (eGFR) <30mL/min/1.73m², or serum creatinine >2.5mg/dL, or participant has proteinuria >3g/day, or protein:creatinine ratio >340mg/mmol at the Screening Visit.

31a. Study participant has any significant hematologic abnormalities at the Screening Visit (Visit 1) as follows:

- a. Hemoglobin <7.0g/dL
- b. █ T-lymphocytes <200/mm³
- c. Absolute neutrophil count <500/mm³
- d. █ T lymphocytes <500/mm³ in combination with neutrophil count <1000/mm³
- e. Platelets <25,000/mm³. Study participants with a higher platelet count should also be excluded if they have a clinical risk of bleeding for reasons other than SLE.

Note: Study participants with an isolated laboratory parameter outside of the normal range at the Screening Visit may have a repeat test. If the repeat laboratory parameter is within normal range, the study participant may be randomized at the Baseline Visit, provided they meet all other eligibility criteria.

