Events Meeting the AE Definition

• Any abnormal laboratory test results (hematology, clinical chemistry, or urinalysis) not related to SLE or other safety assessments (eg, ECG, radiological scans, vital signs measurements not related to SLE, including those that worsen from baseline, considered clinically significant in the medical and scientific judgment of the Investigator (ie, not related to progression of underlying disease).• Exacerbation of a chronic or intermittent pre-existing condition other than SLE including either an increase in frequency and/or intensity of the condition.• New conditions not SLE related detected or diagnosed after study medication administration even though it may have been present before the start of the study.• Signs, symptoms, or the clinical sequelae of a suspected drug-drug interaction.• Signs, symptoms, or the clinical sequelae of a suspected overdose of either study medication or a concomitant medication. Overdose per se will not be reported as an AE/SAE unless it is an intentional overdose taken with possible suicidal/self-harming intent. Such overdoses should be reported regardless of sequelae.• "Lack of efficacy" or "failure of expected pharmacological action" per se will not be reported as an AE or SAE. Such instances will be captured in the efficacy assessments. However, the signs, symptoms, and/or clinical sequelae resulting from lack of efficacy will be reported as SAE if they fulfil the definition of a SAE.

Events NOT Meeting the AE Definition

- Any clinically significant abnormal laboratory findings or other abnormal safety assessments which are associated with the underlying disease (SLE) except it fulfills seriousness criteria.
- SLE or expected progression, signs, or symptoms of the SLE except they fulfill seriousness criteria.
- Medical or surgical procedure (eg, endoscopy, appendectomy): the condition that leads to the procedure is the AE.
- Situations in which an untoward medical occurrence did not occur (social and/or convenience admission to a hospital).
- Anticipated day-to-day fluctuations of pre-existing disease(s) or condition(s) present or detected at the start of the study that do not worsen.

This document cannot be used to support any marketing application and any extensions or variations thereof.
PUBLIC COPY

Definition of SAE

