Exclusion	30a	Study participant has chronic kidney failure stage 4, manifested by estimated glomerular filtration rate (eGFR) <30 mL/min/1.73m ² , or serum creatinine >2.5 mg/dL, or participant has proteinuria >3 g/day, or protein:creatinine ratio >340 mg/mmol at the Screening Visit.	To protect study participants' well-being. Components of DZP are secreted through the renal system. So far there are only data up to a creatinine clearance of ≥ 45 mL/min/1.73m ² and proteinuria ≤ 3 g/day and no impact could be detected. As Proteinuria is common in SLE study participants this was extended to not

Criterion	N	Content	Justification
			exclude study participants with high unmet medical need but only by a justifiable range
Exclusion	31a	
Study participant has any significant hematologic abnormalities at the Screening Visit (V1) as follows:
 
a. Hemoglobin <7.0g/dLb. █ T-lymphocytes <200/mm³c. Absolute neutrophil count <500/mm³d. █ T lymphocytes <500/mm³ in combination with neutrophil count <1000/mm³e. Platelets <25,000/mm³. Study participants with a higher platelet count should also be excluded if they have a clinical risk of bleeding for reasons other than SLE.	To protect study participants' well-being. Hematological alterations are common in SLE however severe anemia (Hb <7g/dL) and/or thrombopenia (CTCAE grade 4, <25,000/ μ L) is associated with an increased risk for cardiovascular, constitutional and bleeding events. Severe lymphopenia and granulocytopenia or combination is increasing the risk for serious infections which could be exacerbated by DZP.

This document cannot be used to support any marketing authorization application and any extensions or variations thereof.

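### SAP 10.3 derives CTCAE laboratory grades but only lists them, so no readable safety table counts, by arm, participants whose grade worsened from Baseline

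*SAP*

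**What the plan says.** SAP Section 10.3 sets up the grading: "In addition, laboratory values will be graded (where possible) according to CTCAE Version 5.0". It then gives the grade a single destination: "The flag and the CTCAE grade will be included in the listings".

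The categorical tables rest on a different classification: "Shift tables by markedly abnormal lab parameters (see Section 13.18) will be presented for clinical chemistry, hematology parameters". For each of chemistry and hematology there is one table for low values and one for high values, each giving the "number and percentage of participants who have a marked abnormal value at any time of the study post Baseline compared to Baseline". A second output follows: "The number and percentage of participants with a treatment-emergent markedly abnormal result will be presented for each parameter where markedly abnormal criteria are defined". It is broken down by visit and treatment group, with an any-time tabulation.

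The same section also plans summaries of absolute value, change and percent change, figures of means by visit, and full listings.

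Protocol Section 5.2, criterion 31a, sets the hematology entry limits at Screening. Exclusion starts at "Hemoglobin <7.0g/dL", at neutrophils below 500/mm3 (or below 1000/mm3 together with a low T-lymphocyte count), and at platelets below 25,000/mm3. Appendix 13 gives the reason: "Hematological alterations are common in SLE however severe anemia (Hb <7g/dL) and/or thrombopenia (CTCAE grade 4". The parenthesis goes on to give the same 25,000 figure for platelets.

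**The concern.** The trial admits people with substantial cytopenia, and Appendix 13 says that low lymphocyte and granulocyte counts raise an infection risk that the study drug could add to. For these participants the useful safety question is whether counts got worse on drug more often than on placebo. A marked/not-marked table cannot answer that for anyone already marked at Baseline, because the category has no room below it. The CTCAE grade, which does have levels, is derived and then left in the listings.

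AE tables fill the gap only in part. Protocol Appendix 3 (Section 10.3) lists this among the occurrences that do not count as AEs: "Any clinically significant abnormal laboratory findings or other abnormal safety assessments which are associated with the underlying disease (SLE) except it fulfills seriousness criteria". Protocol Section 8.3 likewise has worsening SLE manifestations recorded as AEs only when serious.

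**Working it through.** The plan gives no figure to reproduce here. The check is a classification of example paths under assumed limits.

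**Inputs.** Platelet entry limit 25,000/mm3 (Protocol 5.2). Grade 4 anchor: below 25,000 (Protocol Appendix 13). Marked limit L: not readable, so assumed at 75,000, 50,000, 40,000 and 25,000/mm3. The platelet paths are hypothetical; each runs from the Baseline value to the lowest post-Baseline value.

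**Rule.** A value is marked (M) if it is below L, otherwise not (N). The shift cell is Baseline status to any-time post-Baseline status. A single level for low values is assumed.

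| Path (per mm3) | Passes into grade 4 by the protocol's anchor? | L = 75,000 | L = 50,000 | L = 40,000 | L = 25,000 |
|---|---|---|---|---|---|
| 45,000 to 10,000 | yes | M to M | M to M | N to M | N to M |
| 45,000 to 48,000 | no | M to M | M to M | N to N | N to N |
| 30,000 to 20,000 | yes | M to M | M to M | M to M | N to M |
| 28,000 to 10,000 | yes | M to M | M to M | M to M | N to M |
| 150,000 to 30,000 | no | N to M | N to M | N to M | N to N |

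**Reading the table.**
- The first two paths share a cell at any limit above 48,000, since both Baseline values and both post-Baseline values then lie below L. At any limit above 45,000 the fall to 10,000 shows no movement.
- At 40,000 the first path does shift, but the third and fourth do not.
- At 25,000 all three falls into grade 4 register, but the drop from 150,000 to 30,000 does not count.
- A single limit therefore misses one kind of worsening or another. Which kind depends on a number that cannot be seen here.

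**Who can be past the limit at Baseline.** Any platelet limit above 25,000 leaves a band of eligible participants below it. Even at 25,000, footnote i of the Schedule of Activities says that laboratory results are not available for confirming eligibility at Visit 2. SAP Section 3.4 takes the last pre-infusion value as Baseline, so a Baseline value can lie below the Screening limit.

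**Comparison within the SAP.** Table 10-3 uses three QTcF bands plus change bands. Table 10-1 combines level and change for pulse and blood pressure. Section 10.3 gives the urinary ratios a separate summary in participants with a raised protein:creatinine ratio at Baseline. The readable text has nothing comparable for hematology.

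**The case against.** The strongest objection is that Section 13.18 is redacted. It may hold several levels or a worsening-from-Baseline rule, and Section 10.3 does not show how the treatment-emergent table treats someone already abnormal at Baseline. Redaction is not a defect in the plan. This stands: the point has to be conditional on a single limit per direction, and it cannot be said as fact that some participants will be marked at Baseline.

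A reader might also infer that worsening cytopenia could go unseen. The documents do not support that, for these reasons:
- Change and percent-change summaries carry minimum and maximum by arm, and listings show value, change, flag and grade for each participant.
- Cytopenia ascribed to SLE feeds the BILAG hematology system, for which the SAP plans grade shifts and organ-system worsening by visit. SLEDAI-2K has thrombocytopenia and leucopenia items.
- Protocol Section 8.2.4 treats an SLE-associated laboratory finding as clinically significant when it is judged worse than expected. Appendix 3 names blood dyscrasias among important medical events that are usually serious. A fall to 10,000 platelets could well be reported by that route.
- The IDMC reviews safety data at least every six months.

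These outputs limit the consequence but do not supply the missing count. A minimum is one extreme value and a mean is an average. BILAG is an efficacy instrument and may not move within a grade. The AE route depends on investigator judgment.

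Finally, Protocol Section 9.4.1 leaves the form of laboratory summaries to the SAP, so nothing is contradicted. That is correct; this is an improvement in tabulation, not the repair of an inconsistency.

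**Conclusion.** The point holds in a limited form. In the readable SAP, CTCAE grades are derived but reach only listings, and no readable safety table counts participants per arm whose grade worsened. If Section 13.18 sets one limit per direction, the shift table cannot separate improvement from deterioration in a participant who starts past the limit and stays past it. The entry rules allow such participants.

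Its size cannot be put in numbers: the documents give neither the limits nor the Baseline distribution of laboratory values, so any count of affected participants would be a guess. The gap concerns one safety tabulation, and no efficacy endpoint or hypothesis test depends on it. It is worth fixing because the fix is cheap and the participants concerned are those whose further worsening matters most.

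**What to change.** In SAP Section 10.3, for CTCAE-gradable hematology and chemistry parameters, add a by-arm shift table of Baseline grade by worst post-Baseline grade. Show separately the number and percentage with an increase of at least one grade and with an increase to grade 3 or higher. If Section 13.18 already provides graded levels that do this, a sentence in Section 10.3 saying so is enough.

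Also state how the treatment-emergent markedly abnormal table handles participants who are markedly abnormal at Baseline: excluded, counted on any further marked value, or counted only on defined worsening.

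The cost is one extra table built from grades already derived for the listings. It needs no new data and no protocol amendment.

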10.4 Vital signs, physical findings, and other observations related to safety

10.4.1 Vital signs

The following vital signs measurements will be assessed:

- Pulse rate (PR) (bpm)
- Systolic blood pressure (SBP) (mmHg)
- Diastolic blood pressure (DBP) (mmHg)
- Respiratory Rate (breaths per minute)
- Body temperature (°C)
- Body weight (kg)
- Body height (cm)
- BMI (kg/m²)

Vital sign will be analyzed in the SS for observed cases, where all data is included. Absolute values and Changes from Baseline for pre-infusion vital signs measurements will be presented by visit. Additionally, changes from pre-infusion to post-infusion time points at infusion visits will be summarized.

Listings will be provided of vital sign measurements by visit and timing relative to dosing. It will include the change from the Baseline visit for pre-infusion vitals at each post-Baseline visit, as well as changes from pre-infusion to post-infusion time points within visits. The listing will also include details of abnormal values.

Vital signs with values below the lower limit of normal and a decrease greater than the limit given in the following table or vital signs with values above the upper limit of normal and an increase greater than the given value in the table will be classified as abnormal.

A summary of the number and percentage of participants with a vital sign abnormality will also be provided by vital sign measurement, by visit and overall.

Please see below for abnormality criteria for vital sign and body weight parameters:

Table 10-1: Abnormality criteria for vital sign parameters

PARAMETER	AGE RANGE	ABNORMALITY CRITERIA
Pulse Rate (beats/minute)	≥16y	<45 and a decrease from Baseline of ≥15 >90 and an increase from Baseline of ≥15
Systolic Blood Pressure (mmHg)	≥16y	<90 and a decrease from Baseline of ≥15 >140 and an increase from Baseline of ≥15
Diastolic Blood Pressure (mmHg)	≥16y	<40 and a decrease from Baseline of ≥15 >90 and an increase from Baseline of ≥15
Respiratory Rate (breaths/min)	≥16y	<10 >25
Body Temperature (°C)	≥16y	<35.9 >37.6

Abbreviations: m = month, y = year. A month is defined as 30.44 days; a year is defined as 365.25 days.

Table 10-2: Abnormality criteria for body weight

PARAMETER	AGE RANGE	ABNORMALITY CRITERIA
Body weight (kg)	≥16y	≥10% decrease from Baseline ≥10% increase from Baseline

10.4.2 **Electrocardiograms**

Electrocardiogram data are collected at Visit 1, Visit 2, Visit 3, Visit 8 and Visit 14. ECGs will be analyzed in the SS for observed cases, where all data is included. ECG outcomes (as determined by investigators) will be listed by participant, visit, and timing relative to dosing.

A summary table of treatment emergent ECGs values (quantitative parameters as provided by central readers, including observed value and change from Baseline) will be presented displaying descriptive statistics by visit. This data will also be listed.

Outlier analysis (eg, QTcF, PR, QRS and HR) using central readers data will be provided (see [Table 10-3](#) for details). The number and percentage of participants with an outlier at any post-BL time point will be presented by treatment group for each parameter.

A summary of the number and percentage of participants with a treatment emergent ECG finding (as provided by central readers) at the Baseline visit, and any post-Baseline time point by treatment will also be provided.

Abnormal ECGs and findings (as determined by central reader) will be listed by participant, visit, and timing relative to dosing.

The overall assessment provided by sites (investigators) will not be used for table summaries but will be presented in participant data listings.

Table 10-3: Abnormal criteria for ECG parameters

PARAMETER	AGE RANGE	ABNORMALITY CRITERIA
QTcF	≥16y	Treatment-emergent value of >450 and ≤480 ms when not present at Baseline (new onset) Treatment-emergent value of >480 and ≤500 ms when not present at Baseline (new onset) Treatment-emergent value of >500 ms when not present at Baseline (new onset) Increase of QTcF from Baseline of >30 and ≤60 ms Increase of QTcF from Baseline >60 ms
PR	≥16y	Increase of PR from Baseline >25% resulting in PR >200 ms
QRS	≥16y	Increase of QRS from Baseline >25% resulting in QRS >100 ms
HR	≥16y	Decrease of HR from Baseline >25% resulting in HR <50 bpm Increase of HR from Baseline >25% resulting in HR >100 bpm

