8.1 Efficacy assessments

8.1.1 Clinical assessments of disease activity

8.1.1.1 BILAG 2004

The BILAG 2004 will be used as a clinical assessment of SLE disease activity (Tsokos et al, 2007).

The Investigators will perform an anamnesis and physical examination at every visit and will record present symptoms corresponding to the BILAG 2004 components in the electronic clinical outcomes assessment (eCOA). Clinical features attributable to SLE are to be recorded and based on the study participant's condition in the last 4 weeks compared with the previous 4 weeks. For vital signs and laboratory parameters, Investigators must indicate whether or not values are outside the normal range and, if outside the normal range, whether or not they are due to SLE.

Nine body/organ-based systems will be assessed if SLE symptoms are present:

- Constitutional (fatigue, fever, anorexia, weight loss, etc)
- Mucocutaneous (rash, alopecia, mucosal ulcers, etc)
- Neuropsychiatric (headache, seizure, psychosis, etc)
- Musculoskeletal [REDACTED] etc)
- Cardiorespiratory (coronary vasculitis, cardiac failure, effusion, etc)
- Gastrointestinal (lupus enteritis, hepatitis, peritonitis, etc)
- Ophthalmic (keratitis, scleritis, optic neuritis, etc)
- Renal (proteinuria, urine microscopy for red blood cells, casts, etc)
- Hematology (cytopenias, coagulopathy, etc)

The Investigator must maintain/provide independent supporting source documents (eg, chart, worksheet, clinic notes, labs, and photodocumentation of cutaneous SLE manifestations) capable of withstanding audit:

- For each SLE symptom present at the visit or present within the past 4 weeks before the visit
- Indicating if symptom had a new onset, was improving, same, or worse in the past 4 weeks as compared to the prior 4 weeks
- Sufficient descriptive detail to support changes (improved, worsening); eg, number/location of arthritic joints, size/location of rashes, etc
- Information indicating that other symptoms relevant for BILAG were not present at the time point of the visit and within the 4 weeks prior to the visit

[figure not shown]
The Sponsor will provide centralized grading (A, B, C, D, and E) based on BILAG 2004 eCOA pages completed by the Investigator, eCRF pages completed by Investigators, laboratory parameters, and may be subject to adjudication. Prior to Visit 2, the site must have received

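### SAP Table 10-3 scores a fall into a lower QTcF band as new onset, and the vital-sign rule in SAP 10.4.1 does not match its own Table 10-1

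*SAP*

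**What the plan says.** **Vital signs (SAP 10.4.1 and Table 10-1).** The text sets two conditions for an abnormality. On the low side: "Vital signs with values below the lower limit of normal and a decrease greater than the limit given in the following table". The high side mirrors it, with the same label of abnormal: "vital signs with values above the upper limit of normal and an increase greater than the given value in the table will be classified as" (final word omitted). For pulse and blood pressure, Table 10-1 gives both a cut-off and a change, for example "<45 and a decrease from Baseline of ≥15" for pulse and ">140 and an increase from Baseline of ≥15" for systolic pressure. For respiratory rate it gives only below 10 or above 25, and for temperature only below 35.9 or above 37.6 °C. The output, which is also given across all visits, is described so: "A summary of the number and percentage of participants with a vital sign abnormality will also be provided by vital sign measurement, by visit and" (final word omitted).

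**QTcF (SAP 10.4.2 and Table 10-3).** Two of the three bands are closed at both ends: "Treatment-emergent value of >450 and ≤480 ms when not present at Baseline (new onset" and "Treatment-emergent value of >480 and ≤500 ms when not present at Baseline (new onset" (closing bracket omitted in both). The third has the same form for values above 500 ms. Separate rows count increases of more than 30 up to 60 ms, and of more than 60 ms. The output is the number and percentage of participants with an outlier at any time after Baseline, by treatment group.

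**The concern.** The QTcF bands do not overlap, and the Baseline condition refers to the band itself. A participant who starts in a higher band and comes down was not in the lower band at Baseline, so the literal rule counts an improvement as a new prolongation. The documents do not rule this case out. The protocol's exclusion criteria set no QTc limit, and Investigators judge Screening ECGs for eligibility (footnote m to Table 1-2).

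In 10.4.1 the sentence and the table give different answers. For respiratory rate and temperature the sentence refers to a change limit that the table does not contain. For pulse and blood pressure the sentence uses a strict inequality and the table does not. Two programmers working from the same SAP could therefore produce different abnormality tables. At stake is whether the counts in two safety outputs are reproducible and mean what their labels say.

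**Working it through.** The plan states no figure to reproduce here. The check applies the rules as written to pairs of Baseline value b and post-Baseline value v.

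**1. QTcF.** The bands are: (1) above 450 to 480 ms; (2) above 480 to 500 ms; (3) above 500 ms. The rule as written flags band k when v is in band k and b is not. The alternative flags band k when v is in band k and b is at or below the band's lower bound.

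| b → v (ms) | As written | With Baseline ceiling |
|---|---|---|
| 440 → 470 | new onset, band 1 | same |
| 470 → 490 | new onset, band 2 | same |
| 470 → 470, 490 → 490, 510 → 510 | not flagged | same |
| 490 → 470 | new onset, band 1 | not flagged |
| 510 → 470 | new onset, band 1 | not flagged |
| 510 → 490 | new onset, band 2 | not flagged |

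Over all whole-millisecond pairs from 400 to 550 ms, the falls flagged as written number:

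- band 1: 30 values of v (451 to 480) × 70 values of b (481 to 550) = 2,100
- band 2: 20 values of v (481 to 500) × 50 values of b (501 to 550) = 1,000
- total: 3,100

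With the ceiling the total is 0, and every rising pair keeps its classification. Band 3 contributes nothing, because no higher band exists to fall from. These are logical cases, not participants.

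**2. Participants affected by the QTcF rule.** A fall can be flagged only if Baseline exceeds 480 ms, so the excess cannot exceed the number of such participants. With the planned 312 randomised, each 1% with Baseline above 480 ms gives at most 0.01 × 312 = 3.12. The documents give no QTcF distribution. A simulation assumed normal person-level means plus visit-to-visit noise, an overall mean of 415 to 425 ms, an SD of 20 to 25 ms, and three post-Baseline ECGs (Weeks 4, 24 and 48). It gave an excess of about 0.15, 0.9 and 3.9 per 312 in three scenarios. The result depends on the tail above 480 ms and shows only the order of magnitude.

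**3. Vital signs.**

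| Baseline → post-Baseline | Table 10-1 | Sentence in 10.4.1 |
|---|---|---|
| Temperature 37.7 → 37.7, or 38.2 → 37.7 | abnormal | no limit supplied; not abnormal if any rise is required |
| Respiratory rate 26 → 26, or 30 → 26 | abnormal | as above |
| Pulse 95 → 95, systolic 150 → 150 | not abnormal | not abnormal |
| Pulse 80 → 95, systolic 130 → 145, diastolic 80 → 95 (change exactly 15) | abnormal | not abnormal |

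**4. A possible repair that fails.** Suppose Table 10-1 excluded anyone already outside the same temperature or respiratory limit at Baseline. Then 37.7 → 40.0 °C and respiratory rate 26 → 40 would go unflagged. A temperature simulation assumed mean 36.5 to 36.6 °C, between-person SD 0.20 to 0.25, within-person SD 0.25 to 0.35 and 12 readings. In it, 44 to 59% of the participants that this exclusion removes had an out-of-range reading worse than Baseline. Only 3 to 5% of all flagged participants never had one.

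**The case against.** **The table may be meant to govern.** SAP 10.4.1 refers the reader to the tables for the abnormality criteria, and absolute cut-offs for respiratory rate and temperature can be deliberate. The output counts participants with an abnormality, not a new one, and 37.7 °C is outside the stated limit. This stands. It is a reason to correct the sentence rather than add a Baseline condition to the table. It does not remove the mismatch.

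**The labels treatment-emergent and new onset may imply worsening.** A careful programmer might read them so. However, SAP 10.1 defines treatment-emergent for adverse events by onset date, no definition is given for ECG values, and 10.4.2 even applies the term to findings at the Baseline visit. The PR, QRS and HR rows all state a direction of change, whereas the QTcF bands do not. The intent is probably worsening, but the rule does not say so.

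**Other outputs cover the same ground.** Changes from Baseline, pre- to post-infusion changes, adverse events starting on the day of or the day after an infusion, and infusion reactions are all summarised separately, and the QTcF increase rows are unaffected. This stands and limits the consequence.

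**Stronger readings.** A reader might infer three things that the documents do not support.

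- *Unchanged participants are counted as QTcF outliers.* They are not: an unchanged value stays in its band.
- *The temperature rows wrongly count people who did not worsen.* The output makes no claim of new onset.
- *A treatment effect on lupus fever could mask drug-related fever.* The protocol's BILAG section does list fever ("Constitutional (fatigue, fever, anorexia, weight loss, etc"), but the offset is speculative. A Baseline condition would not remove it, because preventing new lupus fever would still lower the count.

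**Conclusion.** Both faults are real, visible in unredacted text, and minor. Two of the three QTcF bands misclassify a fall as new onset on their literal wording. The 10.4.1 sentence cannot be applied to respiratory rate and temperature, and it disagrees with Table 10-1 at a change of exactly 15.

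The logical result needs no assumption. The size does: the QTcF excess is bounded by the number of participants with Baseline above 480 ms, and is probably between none and about four of 312 under the assumed distributions. The protocol's bundle-branch-block row (7.1.2) anticipates Baseline values of 450 to 480 ms. It stops short of the range where the rule misfires, so it does not show that such participants will be enrolled.

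The tables are descriptive, use the Safety Set and apply the same rules in both arms. The point does not touch the primary analysis.

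**What to change.** **Table 10-3.** Define new onset as a higher QTcF category than at Baseline:

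- above 450 to 480 ms, with Baseline at or below 450 ms
- above 480 to 500 ms, with Baseline at or below 480 ms
- above 500 ms: leave as it is, since the present wording already means Baseline at or below 500 ms

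**SAP 10.4.1.** Use ≥ in the sentence, as Table 10-1 already does. State that, within Table 10-1, the change condition applies to pulse and to systolic and diastolic pressure, and that respiratory rate and temperature are judged on the absolute cut-offs alone.

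**Pre-existing versus new abnormality.** If this distinction is wanted for respiratory rate and temperature, present those two by Baseline status in a shift layout, as SAP 10.3 does for markedly abnormal laboratory values. Do not exclude participants who were outside the limit at Baseline.

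The cost is one amended sentence, two amended table entries and a small programming change, plus one shift display if chosen. No new data are needed.
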